3.1. Inclusion Criteria

- ≥18 years of age
- Comatose (do not follow simple verbal commands)
- Have any initial heart rhythm (shockable or non-shockable)
- OHCA including the emergency department

3.2. Exclusion Criteria

- Name on EFIC opt-out list
- In-hospital cardiac arrest
- Interval >6 hours from ICU admission at an enrolling center to study drug initiation
- Hemoglobin less than 7.0 g/dL or requiring a transfusion
- Pregnant patients
- Preexisting terminal disease making 180-day survival unlikely
- Refused informed consent
- Emergent coronary artery bypass grafting
- Anaphylaxis or angioedema to beta-lactam antibiotics (i.e., cephalosporins or penicillins)
 - o Beta-lactam allergies listed without a known reaction will not be an exclusion
- Under legal guardianship or prisoner
- Clinical *bacterial* infection prior to hospital admission defined as any one of the following:
 - Infectious prodrome preceding OHCA
 - o Active course of antibiotics for infection prior to admission
 - o Active infection documented in the electronic medical record
 - Family or surrogate endorsement of an active infection
- Active course of antibiotics for infectious or non-infectious indications
 - A single dose of an antibiotic that is NOT ceftriaxone is acceptable prior to randomization as long as the bedside treatment team does not intend to continue the antibiotic(s)
- Indication for antibiotics at the time of screening in the opinion of the bedside treatment team
- Non-English speaking
- Goals of care are not clear at the time the screening window closes and the subject is not enrolled through the EFIC pathway
- Survival through 48 hours after ROSC is unlikely to occur

3.3. Inclusion Window

The optimal time from OHCA to antibiotic initiation is unclear. Theoretically, the sooner it is administered, the more effective it may be. Prospective, controlled studies in heterogeneous cohorts of acutely brain-injured patients used four or six hours from intubation or six hours from ICU admission.¹⁹⁻ ²¹ The ANTHARTIC trial, which included OHCA patients, used <6 hours from ROSC to randomization.³ Accordingly, patients will enrolled if ≤6 hours has passed since ICU admission to study drug initiation.

3.4. Methods of Recruitment

All OHCA patients are admitted through the emergency department or directly to the ICU at XXXX. An order set or power plan for TTM within the electronic medical record is activated for all comatose OHCA patients. Order set activation sends an automated email to study investigators and research coordinators who screen patients 24 hours a day 7 days a week. LAR will be approached for informed consent, or the EFIC process will be initiated in their absence at XXXX only.

3.5. Screening

Screening will be performed in the emergency department, cardiac angiography suite, ICU or via telephone using a standard script. A screening log will be maintained for OHCA patients, whether they are enrolled or not, and the reason for exclusion. Screening logs will be only available to approved personnel.

3.6. Informed Consent

Study investigators will approach the patient's Power of Attorney for Health Care (POAHC) or LAR to provide informed consent. Patients regaining consciousness will be asked for informed consent as soon as they are able to make a decision and have the capacity to do so. Consent may be obtained in person or via remote consent process.

In the event a patient's POAHC or LAR cannot be reached for informed consent within 30 minutes, the EFIC process will be initiated at XXXX only per the Food and Drug Administration's Guidance for Institutional Review Boards, Clinical Investigators, and Sponsors on Exception from Informed Consent Requirements for Emergency Research.³⁶ The requirements for a clinical trial to incorporate EFIC are as follows:

- The human subjects are in a life-threatening situation that necessitates urgent intervention;
- Available treatments are unproven or unsatisfactory;
- Collection of valid scientific evidence is necessary to determine the safety and effectiveness of the intervention;
- Obtaining informed consent is not feasible because the subjects are not able to give their informed consent as a result of their medical condition;
- The intervention must be administered before consent can be obtained from the subject's legally authorized representative;
- There is no reasonable way to identify prospectively individuals likely to become eligible for participation;
- Participation in the research holds out the prospect of direct benefit to the subjects; and
- The clinical investigation could not practicably be carried out without the waiver.

After a thorough community consultation and public disclosure, the IRB at XXXX deemed it was appropriate to conduct the trial. The EFIC process will be initiated after 30 minutes of trying to contact the POAHC or LAR

Subsequent to an EFIC enrollment, efforts to contact an LAR will continue. The research team will inform LAR at earliest opportunity of the subject's inclusion in the trial, the details of the investigation, other information in the informed consent document and consent to continue in the study will be sought. The LAR will be also be notified that they may discontinue the patient's participation without penalty or loss of benefits to which the subject is otherwise entitled. Patients enrolled in the study through the EFIC

process or LAR consent will be asked for informed consent as soon as they have the capacity to do so, preferably prior to hospital discharge.

3.7. Randomization

A computer-generated allocation sequence will randomize patients in a 1:1 ratio in blocks of six. The clinical trials pharmacist at xxxx will be responsible for randomizing patients independent of study investigators. Based on the randomization, the clinical trials pharmacist will prepare the study drug blinded for delivery to the bedside nurse for administration. At non-xxxx hospitals, the investigators will contact the clinical trials pharmacist at xxxx, or their designee, to tell them of an enrollment. The xxxx clinical trials pharmacist will determine the subject number and complete the randomization.

3.8. Study Drug

Ceftriaxone for injection is a sterile, semi-synthetic, broad-spectrum cephalosporin antibiotic available for IV or intramuscular injection.³⁷ It's chemical formula is C₁₈H₁₆N₈Na₂O₇S₃•3.5H₂O and has a molecular weight of 661.6. It contains 83 mg (3.6 mEq) of sodium per gram of ceftriaxone activity. Study drug will be provided by xxxx.

3.8.1. Preparation

Ceftriaxone 2 gram vials will be obtained from Pfizer, which is XXXX's preferred supplier through its wholesaler. Vials will be reconstituted with 19.2 mL of Sterile Water for Injection (SWFI) resulting in a 100 mg/mL solution. The reconstituted solution is a light yellow to amber in color. After reconstitution with of SWFI, it requires further dilution with 50 mL of 0.9% sodium chloride. Overfill volume of 8 mL will not be removed from the 50 mL of 0.9% sodium chloride bag resulting in a total volume of 78 mL. This will be done to maintain blinding as well.

Matching placebo will be a 50 mL 0.9% sodium chloride bag with 20 mL of SWFI added. Overfill volume of 8 mL in the 0.9% sodium chloride bag will not be removed resulting in a total volume of 78 mL. All injections will be prepared in compliance with United States Pharmacopeia Chapter 797 Guidelines and will be classified as low risk.

3.8.2. Rationale for selection

Ceftriaxone was selected for many reasons: 1) bactericidal activity against commonly isolated bacteria in comatose OHCA patients, 2) generic availability and low cost, 3) ease of administration over 30 minutes, 4) favorable local susceptibility profile, 5) excellent safety data, and 6) potentially neuro-protective.³⁷

Although informative, data from the TTM trial included isolates through 14 days of admission and ANTHARTIC through 7 days of admission.³ Prophylactic antibiotics are intended to prevent EOP due to less resistant, community-acquired bacteria. Bacteria isolated after 72-96 hours of ICU admission tend to be more resistant and healthcare-associated.³⁸

Bacteria	TTM Trial ¹	ANTHARTIC Trial ¹	xxxx Ceftriaxone Susceptibility ²
Gram-positive			
Staphylococcus aureus	22.9%	12%	86%
Streptococcus pneumoniae	5.5%	7%	99%
Streptococcus agalactiae	1.5%	3%	not reported
Gram-negative			
Haemophilus influenzae	9.1%	22%	100%
Escherichia coli	9.1%	11%	93%
Klebsiella pneumoniae	5.1%	4%	94%
Serratia marcescens	5.1%	3%	89%
Klebsiella oxytoca	3.6%	1%	97%
Enterobacter cloacae	3.3%	3%	78%
Pseudomonas aeruginosa	2.5%	3%	not active
Enterobacter aerogenes	2.2%	2%	75%
Proteus mirabilis	2.2%	1%	98%
Moraxella catarrhalis	1.5%	1%	not reported

¹ Percentages do not equal 100 for each study as some organisms (e.g., fungi) were not included above

² xxxx ceftriaxone antibiogram data through December 2019

TTM = targeted temperature management

The ceftriaxone dose of 2 gm IV q12h was selected using internal antibiogram data at XXXX, as well as the cumulative fraction of response based on dose. These data appear below:

Regimen	Cumulative Fraction of Response
Ceftriaxone 1 gm IV q24h	8%
Ceftriaxone 2 gm IV q24h	45%
Ceftriaxone 2 gm IV q12h	86%

3.8.3. Labeling

In order to maintain blinding, an opaque cover will be placed over the study drug due to its light yellow to amber color.

3.8.4. Distribution and management

Study drug will be kept separate from the pharmacy supply. The clinical trials pharmacist will utilize an accountability form to document study drug inventory. Drug accountability will not be checked during

monitoring visits to maintain blinding. Study drug will be delivered by the clinical trials pharmacist or technician to the bedside nurse for administration.

3.8.5. Return and destruction

Study drug dispensed for an enrolled patient that is not administered will be returned to the pharmacy. At the end of the trial, any remaining inventory will be destroyed by the clinical trials pharmacist.

3.9. Placebo

Matching placebo of 50 mL 0.9% sodium chloride will be dispensed for patients randomized to the control arm. The 50 mL 0.9% sodium chloride bags contain 8 mL of overfill. Another 19.2 mL of SWFI will be added resulting in a total volume of 78 mL. In order to maintain blinding, an opaque cover will be placed over the bag due to ceftriaxone's light yellow to amber color. Placebo will be infused over 30 minutes.

3.10. Blinding and Unblinding

The study will be conducted in a blinded manner including: 1) patient, 2) study investigators/ coordinators, 3) pneumonia adjudication committee, 4) bedside team, and 5) outcome evaluators. The clinical trials pharmacist and members of the Data Safety Monitoring Board (DSMB) will not be blinded.

Unblinding may occur for a serious adverse event or if the bedside treatment team determines it is medically necessary. Results of unblinding will not be communicated to study investigators, members of the pneumonia adjudication committee, or the outcome evaluators. Accidental unblinding will be dealt with on a case-by-case basis and patients may continue in the study depending on the circumstance.

3.11. Outcomes

Outcomes were developed for the present study and to help with a sample size calculation for a definitive trial powered for mortality or functional outcome. They were selected by carefully reviewing prior trials and observational data.

3.11.1. Primary efficacy outcome

• Clinically-diagnosed EOP occurring <4 days after initiation of mechanical ventilation

There are no validated diagnostic criteria for pneumonia in comatose OHCA survivors. Consequently, the definition of clinical pneumonia was adapted from diagnostic criteria for nosocomial pneumonia proposed by the Centers for Disease Control and Prevention/ National Healthcare Safety Network, American Thoracic Society and the Infectious Diseases Society of America, and published definitions of pneumonia in this patient populations.^{3,39,40}

During the 72-hour TTM period, clinical pneumonia will be defined as:

- 1. New or progressive lung infiltrate and at least one of the following (a or b):
 - a. New purulent secretions or change in quantity or quality of sputum
 - b. Worsening gas exchange defined as (any of i through iii):
 - i. Oxygen desaturations or PaO₂ /FIO₂ ≤240
 - ii. Increased oxygen requirements

- Increase in daily minimum FiO2 of ≥0.20 (20 points) over the daily minimum FiO2 of the first day in the baseline period, sustained for ≥ 2 calendar days. Daily minimum defined by lowest value of FiO2 during a calendar day that is maintained for >1 hour.
- iii. Increased mechanical ventilator demand
 - A sustained increase in the daily minimum PEEP of ≥ 3 cmH₂O following a period of stability or improvement on the ventilator. PEEP values from 0 to 5 cmH₂O are considered equivalent. Daily minimum defined by lowest value of PEEP during a calendar day that is maintained for >1 hour.

After the 72-hour TTM period, clinical pneumonia will be defined as:

- 1. New or progressive lung infiltrate and at least two of the following (a through e):
 - a. New purulent secretions or change in quantity or quality of sputum
 - b. Worsening gas exchange defined as (any of i through iii):
 - i. Oxygen desaturations or $PaO_2 / FIO_2 \le 240$
 - ii. Increased oxygen requirements
 - iii. Increased ventilator demand
 - c. Cough, dyspnea, tachypnea, rales or bronchial breath sounds
 - d. Body temperature ≥38°C
 - e. Leukopenia (<4,000 white blood cells/mm³) or leukocytosis (>12,000 white blood cells/mm³)

A clinical diagnosis of pneumonia will be microbiologically confirmed using flexible fiberoptic bronchoscopy with >10⁴ colony forming units (CFU) per mL of pathogenic bacteria or unprotected minibronchoalveolar lavage with >10⁴ CFU/mL of pathogenic bacteria in intubated patients. In non-intubated patients, an expectorated sputum sample will be used. Blinded, board certified pulmonologists will adjudicate any clinical or microbiological pneumonia diagnosis.

3.11.2. Secondary efficacy outcomes

- Days of antibiotic susceptibility coverage
- Microbiologically-confirmed EOP occurring <4 days after initiation of mechanical ventilation
- Microbiologically-confirmed late-onset pneumonia occurring ≥4 days after initiation of mechanical ventilation
- Clinically-diagnosed late-onset pneumonia occurring ≥4 days after initiation of mechanical ventilation
- Incidence of non-pulmonary infections
- ICU-free days in the first 28 days of admission
- Mechanical ventilator-free days in the first 28 days of admission
- ICU LOS
- Hospital LOS
- ICU mortality
- Hospital mortality
- Discharge disposition

- Home with services
- Home without services
- o Rehabilitation
- Skilled nursing care
- Hospice
- o Death
- o Transfer to another hospital
- Functional outcome at hospital discharge and six months post cardiac arrest (+/- 30 days)
 - Good functional outcome will be mRS ≤0-3 of or a CPC 1-2 (Appendices 16.1 and 16.2)
 - Functional outcome will be assessed by a research coordinator at hospital discharge and via telephone at six month follow up

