The ceftriaxone to PRevent pneumOnia and inflammaTion aftEr Cardiac arrest (PROTECT) randomizedcontrolled trial and resistome assessment will evaluate the impact of prophylactic ceftriaxone on earlyonset pneumonia (EOP) in patients resuscitated from out-of-hospital cardiac arrest (OHCA) and are comatose. The trial will build upon the findings from observational studies and the Antibiotherapy during Therapeutic Hypothermia to Prevent Infectious Complications (ANTHARTIC) trial.¹⁻³

The PROTECT trial is a multi-center, randomized-controlled, quadruple-blind, non-commercial superiority trial in which prophylactic ceftriaxone for three days after OHCA will be compared with standard care. The trial will also study ceftriaxone's ability to suppress T-cell-mediated inflammation via increased CD73/ adenosine signaling. It will also determine the effect of prophylactic ceftriaxone on the bacterial resistome using metagenomic sequencing and resistance genotype expression.

Patients ≥18 years of age will be eligible for enrollment if they are admitted to the hospital following OHCA and are comatose. The traditional informed consent process will take place prior to any study procedures. Exception from Informed Consent (EFIC) will be invoked when a family member or legal authorized representative (LAR) is unavailable at xxxx. Bedside clinicians, study investigators, patients and outcome adjudicators will be blinded to group allocation.

All patients will receive guideline-recommended treatment. Targeted temperature management (TTM) at a patient-specific goal may be used. Neurological monitoring may include the bispectral index (BIS) and continuous electroencephalography (cEEG) until it is deemed clinically unnecessary. Seizures will be aggressively treated according to clinical practice guidelines. Sedation and analgesia will be minimized to prevent interference with neurological prognostication while still providing comfort.

Patients will be randomized 1:1 to ceftriaxone 2 gm intravenously (IV) every 12 hours for three days or matching placebo. All other aspects of care will be the same between groups. Patients will undergo shotgun metagenomics sequencing to evaluate their bacterial resistome using nucleic acids obtained from sputum samples and rectal swabs. The impact of ceftriaxone on inflammation will be examined through T-cell-mediated inflammation via CD73/ adenosine signaling.

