2.2. Pneumonia after Cardiac Arrest

Pneumonia is an infection of the lungs resulting in alveolar inflammation and fluid or purulent material accumulation. It is the most common infection after cardiac arrest occurring in up to 65% of patients treated with TTM.⁶ Infections are associated with increased intensive care unit (ICU) length of stay (LOS), hospital LOS, duration of mechanical ventilation, post-discharge rehabilitation need, tracheostomy, and mortality, while also reducing the incidence of a good functional outcome.⁷⁻¹¹

Pneumonia results from aspiration during cardiopulmonary resuscitation (CPR), or by introduction of oropharyngeal flora into the lungs during airway management. It may also be due to gastrointestinal hypoperfusion, which leads to ischemic injury to the intestinal mucosa, bacterial translocation, and hematogenous spread. Infection might also be the result of post-resuscitation immune suppression.¹²⁻¹⁸ The association between infection and morbidity and mortality justifies further study.

Preventing infection after OHCA may: 1) reduce exposure to broad-spectrum antibiotics and subsequent collateral damage, 2) prevent hemodynamic derangements due to local and systemic inflammation, and 3) prevent an association between infection and morbidity and mortality. These benefits must be balanced with the risk for altering bacterial resistomes in the absence of clinical infection. Accordingly, further study is warranted to understand the risk-to-benefit ratio of prophylactic antibiotics.

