5.5. CD73 and Pro-inflammatory Cytokines

Multi-parametric flow cytometric analysis will be conducted on whole blood cells before study drug and on study-day 1 and study-day 3. Cells will be stained with CD4FITC-CD73PeCy7-CD8PerCP-CD3APC/Cy7 following fixation, permeabilized (BD Cytofix/CytopermTM) for intracellular staining with anti-IFN- γ (Clone 25723) or anti-TNF- α (Clone 6402) antibodies (R&D System/Bio-techne). The percentage of CD3+ T cells, CD4+ and CD8+ subpopulations, and CD73 expression on T lymphocytes will be determined within DAPI negative (viable) cell populations using MACSQuant. Myeloid cells will be analyzed to validate ceftriaxone's effect in lymphocytes. Neutrophils and monocytes will be gated and cell surface expression of CD73 and production of TNF- α assayed as described for lymphocytes.

6. Data Collection

Data will be collected to screen, recruit, and determine eligibility of prospective OHCA subjects. Prior to consent, certain information will be gathered for screening including name, date of birth, MRN, date/time of ICU admission, details surround the cardiac arrest, pre-existing terminal disease, medical

history, infection status, allergies, legal guardianship/prisoner, and medical status. Screening logs will be maintained and reasons for exclusion will be recorded. Data collection in REDCap will be completed for patients who are screened and/or enrolled in the PROTECT Study. REDCap is a secure, web-based application for data capture.⁶¹ Data collected may follow the International Liaison Committee on Resuscitation's Utstein criteria for OHCA.⁶² Data will be collected by research coordinators or study investigators from medical records, family members, ambulance run reports, or other sources. The REDCap data collection tool has been modified to ensure demographic data for EFIC patients is captured at XXXX. In addition to the data outline below, information on serious adverse events, study drug and trial completion will be collected.

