6.4. ICU Discharge Data

- Early-onset pneumonia (yes or no)
 - Clinical (yes or no; list criteria for diagnosis)
 - Microbiologically-confirmed (yes or no; list organism and criteria for diagnosis)
- Late-onset pneumonia (yes or no)
 - Clinical (yes or no; list criteria for diagnosis)
 - Microbiologically-confirmed (yes or no; list organism and criteria for diagnosis)
- Non-pulmonary infection (yes or no)
 - List infection and organism, when available
- ICU-free days in the first 28 days of admission (days)
- Mechanical Ventilation duration (days)
- Mechanical ventilator-free days in the first 28 days of admission (days)
- Rearrest in the ICU requiring CPR
- ICU LOS (days)
- ICU mortality (yes or no)
- Date and time of first dose of study drug
- Date and time of last dose of study drug
- Total doses of study drug administered
- Total missed doses of study drug
- Date and times of missed study drug doses
- Study drug discontinuation
- Reasons for study drug discontinuation

• Days of antibiotic spectrum coverage

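### The antibiotic-coverage outcome has two names, no definition and no rule on study drug, and as collected under blind it cannot reflect that only one arm received ceftriaxone

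*Combined protocol and SAP*

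**What the plan says.** Section 3.11.2 opens its list of secondary efficacy outcomes with "Days of antibiotic susceptibility coverage". The data list in Section 6.4 has no item of that name and instead has "Days of antibiotic spectrum coverage". The documents do not define either term: no agents, time window, weighting, favourable direction, handling of death, or rule on study drug.

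Study-drug exposure is held in separate fields of the same Section 6.4 list, including "Total doses of study drug administered", first and last dose times, and missed doses.

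On who records the data, Section 6 states: "Data will be collected by research coordinators or study investigators from medical records, family members, ambulance run reports, or other sources". Those roles are masked under Section 3.10: "The study will be conducted in a blinded manner including: 1) patient, 2) study investigators/ coordinators, 3) pneumonia adjudication committee". The same section adds: "The clinical trials pharmacist and members of the Data Safety Monitoring Board (DSMB) will not be blinded".

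The randomised contrast is itself an antibiotic. Section 1 states: "Patients will be randomized 1:1 to ceftriaxone 2 gm intravenously (IV) every 12 hours for three days or matching placebo".

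Section 9.3 assigns methods to infectious outcomes and to day-28 mortality, and names none for antibiotic coverage. Section 11 says the data will be analysed blind. It describes no step that combines allocation and doses with the coverage item.

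**The concern.** Section 2.2 gives as the first possible benefit of preventing infection that it may "reduce exposure to broad-spectrum antibiotics and subsequent collateral damage". Section 2.5 adds that controls may receive longer broad-spectrum courses because they have more pneumonia. This coverage item is the only listed clinical outcome that could speak to that idea, and Section 3.8 describes ceftriaxone as broad-spectrum. The intervention is therefore part of the exposure in question.

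A field completed under blind can register treatment courses avoided by prophylaxis, but not the prophylaxis itself. If the between-arm difference in that field is read as a difference in overall antibiotic exposure, it can point the opposite way to what patients received. Because the rule on study drug is unwritten, it could also be settled after the results are known, when the choice may decide the sign.

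**Working it through.** **Inputs**
- Early-onset pneumonia (EOP): 55% on placebo, 30% on ceftriaxone, 60 per arm (Section 9.1).
- Smaller effects cited in Section 9.1 from the randomised trial of amoxicillin-clavulanate after cardiac arrest: 34% v 19% at seven days (15 points) and 31% v 17% at five days (14 points).
- Ceftriaxone study-drug days: up to 3 (Section 1). Section 8.3 allows earlier stopping, for example when an infection warrants another regimen.
- *D*, treatment days per EOP: not in the documents. Assumed, and varied from 5 to 14.
- Further assumptions: simple unweighted days; study-drug and treatment days added without overlap; antibiotic use for other reasons equal between arms.

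**Step 1: the plan's own figure.** There is none for this outcome, so the check is on the design rates. With the pooled two-proportion formula at two-sided 5% and 80% power, the mean rate is 0.425 and

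n = [1.96 × √(2 × 0.425 × 0.575) + 0.842 × √(0.55 × 0.45 + 0.30 × 0.70)]² / 0.25² ≈ 60.2, which rounds up to 61 per arm.

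The arcsine formula gives 60, and power at 60 per arm is 79.9%. The sample size reproduces and is not in dispute.

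**Step 2: what a blinded field can carry.** Let *N* be mean non-study antibiotic days and *S* mean study-drug days in each arm. Let *k* = 1 if the recorder counts study drug and 0 if not. A blinded recorder must use the same *k* in both arms, so the recorded difference (ceftriaxone minus placebo) is

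(N_cef − N_pla) + k × (S_cef − S_pla).

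With three days in both arms the second term is k × (3 − 3) = 0. The true difference is (N_cef − N_pla) + 3, because placebo days are not antibiotic days. If early stopping differs by arm, the second term need not be exactly zero, but it still credits placebo patients with saline.

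**Step 3: effect on the sign at 55% v 30%.** Mean days per patient:

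| D | Placebo, 0.55D | Ceftriaxone, non-study, 0.30D | Difference | Ceftriaxone, total, 0.30D + 3 | Difference |
|---|---|---|---|---|---|
| 5 | 2.75 | 1.50 | −1.25 | 4.50 | +1.75 |
| 7 | 3.85 | 2.10 | −1.75 | 5.10 | +1.25 |
| 10 | 5.50 | 3.00 | −2.50 | 6.00 | +0.50 |
| 12 | 6.60 | 3.60 | −3.00 | 6.60 | 0 |
| 14 | 7.70 | 4.20 | −3.50 | 7.20 | −0.50 |

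**Step 4: break-even.** With a mean of *m* ceftriaxone study-drug days, the two versions have opposite signs when D < m / (risk difference):

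| Risk difference | m = 3 | m = 2 |
|---|---|---|
| 0.25 (design) | 12 days | 8 days |
| 0.15 (cited) | 20 days | 13.3 days |
| 0.14 (cited) | 21.4 days | 14.3 days |

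**The case against.** A reader might infer that the plan counts randomised ceftriaxone as zero. The documents contain no such rule; they are silent. Administered doses are recorded, the pharmacist knows the allocation, and analysis follows six months after the last patient's arrest, so study-drug days could be added then. If they are, there is no reversal. That objection stands. What remains is that the plan neither describes this step nor requires it.

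A reader might also infer that the trial is set up to claim reduced exposure. It is not. The hypotheses in Section 2.7 concern EOP, T-cell inflammation and the resistome. Section 2.2 speaks of a possible benefit to be weighed against resistome risk. No text says that lower coverage is favourable, and the outcome's names need not mean simple exposure at all. This too stands, and it is a further reason to define the outcome.

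The 12-day threshold should not be read as a general result. It needs three full study-drug days in every ceftriaxone patient, although Section 8.3 can shorten the course in patients who develop infection. Late-onset pneumonia and non-pulmonary infection might also differ by arm, and an item listed under ICU discharge may be cut off there. A spectrum weighting would change the values.

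Finally, non-study days and total days answer different, legitimate questions. Insisting that the total alone be the main comparison would be a preference about the estimand, not the correction of an error.

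**Conclusion.** The concern holds as a gap in definition and data handling with a possible consequence for the sign. The outcome has two names, no definition, no rule on study drug and no explicitly assigned test. As collected, it cannot carry the randomised difference in ceftriaxone exposure.

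If study drug is left out, the non-study and total comparisons disagree in sign over a wide range of assumed course lengths. At *D* = 7 and the design rates they are −1.75 and +1.25 days per patient. These figures rest on the assumptions listed in the working, above all *D*, which the documents do not supply. They show that the unwritten rule can matter; they do not predict the trial's result.

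Only this secondary outcome is affected. The primary outcome, its analysis and the sample size are not.

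**What to change.** 1. Use one name in Sections 3.11.2 and 6.4. Define it: agents counted, window, any spectrum weighting, favourable direction, and handling of death and ICU discharge.
2. Report two quantities side by side: (a) non-study antibiotic coverage, labelled as such, and (b) total coverage, which adds ceftriaxone study doses actually given.
3. For (b), combine the administered-dose fields in Section 6.4 with allocation after database lock. The pharmacy accountability form is not the right source: it tracks inventory (Section 3.8.4), and dispensed doses may come back unused (Section 3.8.5).
4. Instruct coordinators to leave study drug out of the coverage field, so that (a) is clean and (b) is built only once.
5. Because (b) reveals which arm is which, run it after the blinded analyses under Section 11 are final.
6. Name the test in Section 9.3.
7. Base any statement that prophylaxis reduced overall antibiotic exposure on (b).

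The cost is a short SAP definition and a little more analysis, using data already collected. The result may look less favourable to ceftriaxone.
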